## Severity of the Adverse Event

The severity of AEs, except for AEs for exacerbations, should be graded as follows:

- Mild – usually transient in nature and generally not interfering with normal activities
- Moderate – sufficiently discomforting to interfere with normal activities
- Severe – prevents normal activities.

**Pulmonary Exacerbation:** A pulmonary exacerbation is defined as a new or change in antibiotic therapy (IV, inhaled, or oral) for any 4 or more of the following signs/symptoms:

- Change in sputum
- New or increased hemoptysis
- Increased cough
- Increased dyspnea
- Malaise, fatigue, or lethargy
- Temperature above 38°C (equivalent to approximately 100.4°F)
- Anorexia or weight loss
- Sinus pain or tenderness
- Change in sinus discharge
- Change in physical examination of the chest
- Decrease in pulmonary function by 10%
- Radiographic changes indicative of pulmonary infection

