Treatment with losartan (IND exemption for CF approved): Losartan is an FDA-approved ARB widely prescribed for treatment of hypertension, heart failure, and for renal protection in patients with diabetes. The doses proposed in this study are well tolerated by non-hypertensive patients without significant effect on blood pressure. The most common side effects are fatigue and dizziness. Serious adverse events that are rare include angioedema, hypotension, renal dysfunction or failure, blood dyscrasias, hepatitis, or rhabdomyolysis (clinical assessment of muscle pain). The following should lower the risks to the subjects: The first dose of medication will be administered in the clinic and the patient observed for two hours with blood pressure monitoring. Subjects with hyperkalemia, renal dysfunction, or who are taking potassium supplements will not be enrolled into the study. Participants will be given written descriptions of potential side effects and what to do. For example, mild postural hypotension can be minimized by getting up slowly and maintaining adequate hydration. Skin rashes, palpitations or other moderate or severe adverse events (interference with usual daily activities) without other clear explanation should warrant immediate cessation of treatment and notification of study personnel. There are no drug interactions between losartan and OrkambiTM. Nor are there relevant drug interactions between losartan and or SymdecoTM (by Vertex' drug interaction guidance in their 661 and later clinical trials).

Sweat chloride collection: this is a routine procedure in a CF center and uses a macroduct to collect sweat secretions stimulated by pilocarpine iontophoresis, done according to CFF and CLSI guidelines. The test is well tolerated. A small risk of complications includes mild reddening of the skin. Damage to the skin, such as blistering or burns, occurs very infrequently and this risk can be minimized by careful attention to technique.

Questionnaires, Health History and Physical Examination acquire information that is routinely collected. No significant physical risks arise from these procedures. There is always the risk of psychological distress and breach of confidentiality. In order to minimize this risk, electronic medical records are held in HIPAA compliant password-protected databases, and written information is stored in locked files or file-rooms when not attended by study personnel.

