## **Safety Reporting and Monitoring Plan**

Data monitoring plans will be implemented as follows:

The study will be monitored by Clinical Research Operations & Regulatory Support (CRORS) monitoring group at the University of Miami.

3. Monitoring will occur every 3 months or more frequently if needed.
4. IND exemption for use of losartan in CF patients was granted by the FDA
5. Safety monitoring will be done by the DSMB of the CFFT.
6. Adverse Event Monitoring

- Subjects will be carefully monitored for adverse events (AEs) and serious adverse events (SAEs). Adverse events will be assessed in terms of their seriousness, severity, and relationship to the administration of Losartan.
- All adverse effects will be reported to the co-PIs and discussed with the monitoring group
  - If deemed severe the data will be shared with the DSMB. They will make the decision whether or not to stop the trial.
  - All SAEs will be reported to the DSMB and the appropriate agencies as required.
  - All adverse effects will be reported according to the rules to the FDA, the IRB and to the DMSB

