### Relationship of Adverse Event to Losartan

The assessment of the relationship of an AE to the administration of study drug is a clinical decision based on all available information. An assessment of 'No' would include choices of "not related" or "unlikely related" in the following cases:

1. The existence of a clear alternative explanation, or
2. Non-plausibility (clearly an unrelated circumstance).

An assessment of 'Yes' includes choices of "possibly related" or "related" and indicates that there is a reasonable suspicion that the AE is associated with the use of the investigational drug.

Factors to be considered in assessing the relationship of the AE to study drug include:

- The temporal sequence from drug administration: The event should occur after the drug is given. The length of time from drug exposure to event should be evaluated in the clinical context of the event. We will consider a significant time interval up to 2 hours.
- Underlying, concomitant, intercurrent diseases: Each report should be evaluated in the context of the natural history and course of the disease being treated and any other disease the subject may have (i.e. a pulmonary exacerbation)
- Concomitant medication or treatment: The other drugs the subject is taking or the treatment the subject receives should be examined to determine whether any of them might be suspected to cause the event in question
- Concurrent study procedures: Study procedures should also be considered as possible causes of an AE.

In this study, the investigator will make a separate and independent assessment of every AE's relationship not just to the study drug, but also to concurrent study procedures and to the subject's pre-existing medical condition(s).

A laboratory test abnormality considered clinically relevant, e.g., causing the subject to withdraw from the study, requiring treatment or causing apparent clinical manifestations, or judged relevant by the investigator, should be reported as an AE. Each event should be described in detail along with start and stop dates, severity, relationship to investigational product, action taken and outcome.

Each AE should be followed up until resolution or stabilization as determined by the investigator.

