## **Removal of Subjects from Study**

A subject withdrawal is defined as a discontinuation from the study for any reason. Subjects may withdraw or be withdrawn from this study for the following reasons:

- At their own request or at the request of their authorized representative at any time for any reason
- If, in the investigator's opinion, continuation in the study would be detrimental to the subject's well-being

Also subjects must be withdrawn from the study for the following reasons:

- Subjects with an occurrence of a concomitant disease, or any medical condition which, either because of its severity or duration or necessary change in treatment, contravenes the condition of the study or puts the patient at unnecessary risk or harm.
- Subjects with an occurrence of an AE/SAE which in the opinion of the investigator and/or subject requires termination of treatment. For example, skin rashes, palpitations or other moderate or severe adverse events (interference with usual daily activities) without other clear explanation should warrant immediate cessation of treatment and notification of study personnel.
- Subjects who are noncompliant with the protocol per the investigator's discretion
- Pregnancy
- Severe CF exacerbation during the study as by investigators' discretion.

Subjects who terminate the clinical study prematurely, either at their own request or on the recommendation of the clinical investigator, will be considered early terminations. Subjects who withdraw from the study will not be replaced. Subjects who are discontinued from the study will be requested to return for Early Discontinuation and perform procedures as for visit 8.

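### AE severity is graded only by effect on daily activities, so a symptom-free laboratory abnormality cannot be Moderate or Severe, whatever its size

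*Combined protocol and SAP*

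**What the plan says.** The section Severity of the Adverse Event sets the scope of its scale: "The severity of AEs, except for AEs for exacerbations, should be graded as follows". The grades are "Mild – usually transient in nature and generally not interfering with normal activities", "Moderate – sufficiently discomforting to interfere with normal activities" and "Severe – prevents normal activities". No other severity scale appears.

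Relationship of Adverse Event to Losartan brings laboratory findings into scope. "A laboratory test abnormality considered clinically relevant, e.g., causing the subject to withdraw from the study, requiring treatment" (the sentence goes on to clinical manifestations and investigator judgement) is to be reported as an adverse event, and every event is to be described with its severity.

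Potential Risks lists the rare harms of the drug: "Serious adverse events that are rare include angioedema, hypotension, renal dysfunction or failure, blood dyscrasias, hepatitis, or rhabdomyolysis". Data management says that blood is drawn for liver and renal safety, and Appendix 1 schedules a panel of CBC, CMP and CPK at Visit 1 and, on treatment, at Visits 4, 5 and 7.

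Severity is then used in two places:

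- Safety Reporting and Monitoring Plan: "If deemed severe the data will be shared with the DSMB". The next sentence gives the DSMB the decision on stopping the trial.
- Removal of Subjects from Study: "other moderate or severe adverse events (interference with usual daily activities) without other clear explanation should warrant immediate cessation of treatment". Potential Risks carries the same wording.

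Numeric renal and hepatic limits appear only in the exclusion criteria (creatinine 1.5 times the normal limit, LFTs above 3 times the upper limit). No on-treatment laboratory grade or limit is given.

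**The concern.** The safety panels are drawn to show renal, hepatic, muscle or blood-count harm that a patient may not yet feel. The grade given to what they show depends on what the patient feels. A large silent abnormality and a trivial one get the same grade, and neither meets the severity wording that sends data to the DSMB or that speaks of stopping treatment.

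At stake is the quality of the severity record in a 36-patient trial, and how far escalation of a silent laboratory harm depends on the individual investigator. Faced with a large asymptomatic rise, a site must either record Mild or depart from the written scale. Four sites may choose differently.

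**Working it through.** The plan states no figure on adverse-event severity, so there is nothing to reproduce. The check is to take one case, a patient who feels well but has a clinically relevant laboratory abnormality, through the text.

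1. *Is it an adverse event?* Yes. The Definitions section counts an abnormal laboratory finding, and Relationship of Adverse Event to Losartan requires a clinically relevant one to be reported.
2. *Must it carry a severity?* Yes, under the same section.
3. *Does the activity scale apply?* Yes. Exacerbations are the only exclusion.
4. *Which grade fits?* Severe needs normal activities to be prevented: not met. Moderate needs discomfort that disturbs them: not met. Only Mild is left. Its remark about being transient is qualified, so it does not exclude a persistent abnormality, and persistence alone satisfies neither higher grade. The size of the laboratory value enters none of the three definitions.
5. *Which severity-worded steps are met?* The severe-only DSMB step: no. The wording on moderate or severe events: no, and its own parenthesis repeats the activity criterion. Result: 0 of 2.
6. *Which routes do not depend on the grade?*
   - SAE status at the investigator's discretion (Definitions), with all SAEs going to the DSMB.
   - A general line that all adverse effects are reported to the FDA, the IRB and the DSMB under rules that are not set out (Safety Reporting and Monitoring Plan).
   - Withdrawal when the investigator or subject thinks that treatment must end (Removal of Subjects from Study).
   - Mandatory withdrawal for a medical condition that exposes the patient to needless risk (same section).

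Exposure to the rule, assuming full enrolment, no dropout and no unscheduled tests:

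- Panels per patient on treatment: Visits 4, 5 and 7 = 3.
- Losartan arm: 18 × 3 = 54.
- Both arms, since the sites grade blind: 36 × 3 = 108.
- Sites applying the scale: 36 patients ÷ about 9 per site = 4.

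These count scheduled panels. The documents give no rate of laboratory abnormalities, so no number of misgraded events follows from them.

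**The case against.** The strongest reply is that safety does not hang on the grade. In Removal of Subjects from Study, the sentence on moderate or severe events is an example under a rule based on the investigator's or subject's opinion. In Potential Risks, it follows text on what participants will be told, so it can be read as guidance to patients, who cannot see their own blood results. A separate mandatory withdrawal rule covers conditions that put the patient at needless risk, with no reference to activities. The DSMB receives all SAEs and, by the general line, all adverse effects. Potential Risks itself classes renal dysfunction, hepatitis, blood dyscrasias and rhabdomyolysis as serious. The severe-only step may be meant as escalation on top of routine reporting, and it does not cite the severity scale. Finally, Mild is hedged, so one may say that the scale is silent on laboratory findings and does not order them to be graded Mild.

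Much of this stands. A reader might infer that a silent renal or hepatic injury would go unreported or could not lead to withdrawal; the four routes above rule that out. A reader might also infer that the final report would understate losartan's toxicity in a table by severity; the statistics section plans no such table. CPK should not be called a harm named in the protocol: the named harm is rhabdomyolysis, with a clinical assessment of muscle pain, and CPK is a marker that is drawn. And only clinically relevant abnormalities become adverse events, not every abnormal value.

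The grading defect itself remains. The severity section is the only place where severe is defined, and it takes in laboratory events by its stated scope. If the scale is instead read as silent, sites still have no written way to separate a large silent abnormality from a small one.

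**Conclusion.** The point holds as a defect in severity classification, of minor to moderate weight. As written, a symptom-free laboratory abnormality of any size cannot be graded Moderate or Severe and meets neither severity-worded step. Escalation then rests on investigator judgement and on reporting rules that the protocol does not spell out. The likely result is severity recorded too low, or inconsistently across the four sites.

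The documents do not support a claim that patients are left without a safeguard, that the DSMB is bypassed, or that the reported results would be distorted. The conclusion assumes that sites apply the scale literally and that severe in the monitoring plan has the meaning given in the severity section. How often it would matter cannot be estimated from the documents.

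**What to change.** In Severity of the Adverse Event, limit the activity-based scale to clinical events. Grade laboratory events (creatinine, potassium, liver tests, CPK, blood counts) on a laboratory grading scale that is specified in advance and based on the measured value. Let the scale be specific to each test: multiples of the normal limit do not suit low blood counts and may not suit potassium.

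Then reconcile Potential Risks, Safety Reporting and Monitoring Plan, Relationship of Adverse Event to Losartan, and Removal of Subjects from Study with that scale. State how the severe-only and all-event routes to the DSMB fit together. Say explicitly whether the wording on moderate or severe events refers to laboratory grades at all. Whether and how any grade leads to stopping treatment or to another clinical action is for the sponsor and DSMB to set.

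The cost is amendment wording and one CRF field, with no new samples or visits. The downside is a few more events graded moderate or severe and sent for DSMB review. If the sponsor did link grades to stopping, withdrawals could rise in a trial that does not replace them and whose first analyses use complete cases. That is a reason to settle the link openly and not leave it to be inferred from the new grade.

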## **Removal of Subjects from Study**

A subject withdrawal is defined as a discontinuation from the study for any reason. Subjects may withdraw or be withdrawn from this study for the following reasons:

- At their own request or at the request of their authorized representative at any time for any reason
- If, in the investigator's opinion, continuation in the study would be detrimental to the subject's well-being

Also subjects must be withdrawn from the study for the following reasons:

- Subjects with an occurrence of a concomitant disease, or any medical condition which, either because of its severity or duration or necessary change in treatment, contravenes the condition of the study or puts the patient at unnecessary risk or harm.
- Subjects with an occurrence of an AE/SAE which in the opinion of the investigator and/or subject requires termination of treatment. For example, skin rashes, palpitations or other moderate or severe adverse events (interference with usual daily activities) without other clear explanation should warrant immediate cessation of treatment and notification of study personnel.
- Subjects who are noncompliant with the protocol per the investigator's discretion
- Pregnancy
- Severe CF exacerbation during the study as by investigators' discretion.

Subjects who terminate the clinical study prematurely, either at their own request or on the recommendation of the clinical investigator, will be considered early terminations. Subjects who withdraw from the study will not be replaced. Subjects who are discontinued from the study will be requested to return for Early Discontinuation and perform procedures as for visit 8.

## **Assessment of efficacy**

N/A

## **Quality Control & Quality Assurance**

Monitoring of the study will be provided through the Clinical Research Operations & Regulatory Support (CRORS) monitoring group at the University of Miami.

### **Ethics**

This study will be conducted in accordance with the ethical principles that have their origin in the Declaration of Helsinki and that are consistent with the GCP and applicable regulatory requirements.

The clinical protocol will be submitted to and approved by the UM IRB and will not be initiated until written notification of approval of this study has been received.

IND: because this study will use a medication released on the market but not for this indication, IND exemption was granted for use of losartan in this population.

### **Record Keeping**

Accurate and complete study records from all sites will be maintained and kept at storage facility (Iron Mountain) for a minimum of 6 years after completion of the study.

## **ADMINISTRATIVE SECTION**

### **Protocol Amendments**

Any amendments to the protocol will be approved by the PI and co-investigators. All amendments will be submitted to the IRBs for review and approval prior to implementation unless the amendment details changes related to safety.

### **Protocol Deviations**

The investigator will only make changes to the protocol procedures when necessary to protect the safety, rights, and welfare of the subjects. In such an event where protocol procedures are changed, the investigators are responsible for notifying the IRBs and the internal DSMB.

In the event that an isolated, unforeseen instance occurs resulting in a protocol deviation, the investigators are to document this deviation and notify IRBs as by the rules of the University of Miami, the Cincinnati Children's Hospital Medical Center, the University of Alabama, Birmingham and University of Kansas Medical Center.

### **Case Report Form (CRF)**

All clinical data will be recorded on the CRFs for this study, including their electronics versions (Red Cap).

### Study Documentation and Records Retention

The Good Clinical Practice guidelines issued by the Committee for Proprietary Medicinal Products state that "The investigator must arrange for retention in strict confidence of the subjects' identification codes, names and addresses for at least 15 years after the completion or discontinuation of the trial." Subjects' files and other pertinent documentation (i.e., study protocol, signed informed consent forms, drug dispensing logs, correspondence, and other documents pertaining to the conduct of the study) must be kept for the maximum period permitted by the hospital or private office in accordance with the local requirements, but not less than 15 years.

### **Publication policy**

The results of this research will be disseminated to the scientific community. These results will include results of primary study outcomes and secondary analyses. Priorities in selecting journals and forums for publications submission will be given to peer-reviewed journals as well as presentations and publications of abstracts at national and international scientific meetings. All individuals who have made substantial intellectual, scientific and practical

contributions to this research protocol and the manuscript should, where possible, be credited as authors; all individuals credited as authors should deserve that designation.

**ClinicalTrials.gov Registration**

This trial will be registered at ClinicalTrials.gov

## List of assessments

VISIT	Visit 1	Visit 2	Visit 3 Phone call	Visit 3.a Phone call	Visit 4	Visit 5	Visit 6 Phone call	Visit 7	Visit 8
	-1 weeks	25 mg or 50 mg losartan/placebo	50 mg or 100 mg losartan/placebo	1 week ± 2 days	2 days ± 1 day from Visit 3	3 weeks ± 2 days	6 weeks ± 2 days	10 weeks ± 2 days	13 weeks ± 2 days
Informed consent	X								
Full medical history	X								
Intermittent history		X			X	X		X	X
Physical exam	X	X			X	X		X	X
Vitals	X	X			X	X		X	X
Pulse oximetry	X	X			X	X		X	X
Concomitant medications	X								
Changes in medications		X	X	X	X	X	X	X	X
CFQ-R	X					X		X	
Review adverse events, exacerbations		X	X	X	X	X	X	X	X
Spirometry	X					X		X	
CBC w/ differential; CMP; CPK, CRP and other inflammatory markers	X				X	X		X	
Blood for levels of losartan and metabolites (before next morning dose)						X		X	
NPD	X					X		X	
Leukosorb cytokine levels		X							X
Nasal cells		X							X
Sweat chloride		X							X
Serum or urine pregnancy test	X	X			X	X		X	X

IP dispensation: Visit 2 (3-week supply), visit 4 (3-week supply) and visit 5 (8-week supply)

## Appendix 2

CFQR Questionnaire:

More information:

<http://qol.thoracic.org/sections/instruments/ae/pages/cfq-cfq-r.html>

## **SUMMARY OF CHANGES: Protocol 2.0 dated July 2017:**

This amendment is to make the following modifications on the protocol version 1.0 dated march 2017.

1. Losartan and matching placebo (25 mg or 50 mg pills/ placebo) will be obtained from Hunt Valley Research Pharmacy (Cockeysville, MD) and distributed to the 3 sites, and not from University of Miami Research Pharmacy
2. Dose will be adjusted based on participant's weight at visit 1 as following: If participant's weight is  $< 55$  kg, participant will be randomized to either 25 mg or placebo. If participant's weight is  $\geq 55$  kg, participant will be randomized to either 50 mg or placebo.
3. Blood for levels of losartan and metabolites will be collected before next morning dose and 2 and 6 hours post dose)
4. Monitoring of the study will be provided through the Clinical Research Operations & Regulatory Support (CRORS) monitoring group at the University of Miami.

